8 STATISTICAL METHODOLOGY AND STATISTICAL ANALYSES

8.1 STATISTICAL METHODS

Unless otherwise specified, the following conventions will be applied to all analyses:

- Mean, standard deviation (SD), median, first and third quartiles (Q1 and Q3) values will be formatted to 1 more decimal place than the measured value. Minimum and maximum values will be presented with the same number of decimal places as the measured value.
- Percentages will be rounded to 1 decimal place. Number and percentage values will be presented as xx (xx.x%).
- P-values will be rounded to 4 decimal places. P-values that round to 0.000 will be presented as '< 0.001' and p-values that round to 1.000 will be presented as '> 0.999'.

8.1.1 Analysis of continuous data

Summary statistics will be presented for continuous variables, by way of n, n missing (if any), mean, standard deviation (SD), median, first and third quartiles (Q1 and Q3), minimum and maximum.

8.1.2 Analysis of categorical data

Qualitative/Categorical parameters will be presented in terms of number and percentage of each modality and number of missing and non-missing observations.

Results recorded as "not done" or "unknown" will be considered as missing data and will not be considered in percentage calculation.

8.1.3 Analysis of time-to-event data

Kaplan-Meier estimates (product-limit estimates) will be presented together with a summary of associated statistics including the median survival time with 2-sided 95% CIs. In particular, the survival rate at 3, 6, 9, 12, 15, 18 and 24 months will be estimated with corresponding 2-sided 95% CIs. The CIs for the median will be calculated according

PFIZER CONFIDENTIAL

CT24-WI-GL03-RF02 2.0 *Non-Interventional Statistical Analysis Plan For Primary Data Collection Study*

01-Jun-2020

Page 15 of 28

to Brookmeyer and Crowley (Brookmeyer R, 1982) and the CIs for the survival function estimates at the time points defined above will be derived using the log-log transformation according to Kalbfleisch and Prentice (Kalbfleisch JD, 2002) (conftype=loglog default option in SAS Proc LIFETEST) with back transformation to a CI on the untransformed scale. The estimate of the standard error will be computed using Greenwood's formula.

Frequency (number and percentage) of participants with each event type and censoring reasons will be presented.

For each subgroup analysis, comparison of the different modalities to a reference level will be performed using univariate Cox proportional hazard models. Ties will be handled using the Exact option in SAS (Ties=Exact option in SAS PROC PHREG). Results will be expressed in terms of hazard ratios (HR) and a 2-sided 95% CI will be associated to each HR. A HR of 1 equals a lack of association, a HR greater than 1 suggests an increased risk compared to the reference level, and a HR below 1 suggests a decreased risk.

Time of follow-up for each event (OS and PFS)

A Kaplan-Meier estimation for follow-up duration will also be generated to assess the follow-up time reversing the censoring and event indicators.

Handling of left truncation and right censoring:

The overall survival from the first injection of the chemotherapy used in 1st line will cover

a retrospective and/or prospective data collection period. The time to event of interest ("survival" time) or censoring if no event occurs (right censoring) will be based on the 1st line of chemotherapy start date at a time-point preceding the study entry (avelumab start date). As a result, only participants who are still alive are included in the study.

Therefore, the time from 1st line of chemotherapy start date to avelumab start date is called immortal time and corresponds to a left truncation in survival analyses.

The distribution of an estimator which is both left-truncated and right censored can be estimated using the estimator of Kaplan and Meier (Klein, 1997). The likelihood of conditional survival will be estimated as $S_a(t) = \Pr [X > t \mid X \geq a]$. Occurrence of an event will be studied over time t (the time since the start date) conditional on being free of this event at study entry where a represents the time from the start date to inclusion into the study. This is estimated as follows:

$$\widehat{S}_a(t) = \prod_{a \leq t_i \leq t} \left\{ 1 - \frac{d_i}{Y_i} \right\}, t \geq a$$

where d represents the number of events and Y represents the risk set.

In addition, the Kaplan-Meier estimator does not work well when the size of the risk set is extremely small. This may occur at the end of the curve when right censorings are

PFIZER CONFIDENTIAL

CT24-WI-GL03-RF02 2.0 Non-Interventional Statistical Analysis Plan For Primary Data Collection Study

01-Jun-2020

Page 16 of 28

present and also at the start of the curve if left truncation of data occurs. This latter situation confers early instability in the point estimator of the survival function which may propagate throughout the entire curve. Lai and Ying (Lai, 1991) suggested a solution to this problem by a slight modification of the Kaplan-Meier estimator where events are ignored when the risk set is small:

$$\widehat{S}_a(t) = \prod_{a \leq t_i \leq t} \left\{ 1 - \frac{d_i}{Y_i} I[Y_i \geq cn^a] \right\}, t \geq a$$

where I represents an indicator, n represents the population size and c and a represent constant values. These constant values are used to define a minimum risk set size below which the events are not counted. This minimum risk set size is usually defined in terms of the size n of the study population but for study B9991045, the constants will be set arbitrarily to ensure that the minimum risk set size is equal to 5. The method proposed by Lai and Ying therefore will only be effective for portions of the Kaplan-Meier curve in which the risk set does not exceed 5 participants. This analysis will be performed using the SAS® PROC HPSEVERITY procedure.

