On December 11th, 2020 the CHMP has adopted a positive opinion for avelumab as first line maintenance treatment of adult patients with locally advanced or metastatic urothelial carcinoma whose disease has not progressed with platinum-based induction chemotherapy. Marketing authorization for avelumab use in adv/mUC was issued on January 21st, 2021 by European Medicine Agency.

The early use in France of avelumab in maintenance treatment for adv/mUC patients in the setting of the the ATU is an opportunity to early collect real world data of avelumab in this indication.

In addition to confirm the effectiveness and safety data provided by JAVELIN Bladder 100 study in routine clinical practice this non-interventional study is an opportunity to generate effectiveness and safety data on different subgroups of interest. The main subgroup of interest will be the adv/mUC patients with histological variants. Few data are available on the efficacy of immunotherapy in histology variants of adv/mUC.

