### 9.3. Variables

Table 2 shows the information which will be collected in the study.

090177e1a41aac13\Final\Final On: 28-Jul-2025 13:50 (GMT)

Table 2. Information collected in the study and timing of data collection

Data elements	Variables	Timing of data collection		
		Inclusion	6 weeks	3 months, then every three months until end of follow-up
Inclusion	
 
Type of center
 
Eligibility criteria (inclusion/exclusion)
 
Date of provision of information letter
 
	X		X
Characteristics of patients and their cancer before avelumab initiation	
 
Demographics : month and year of birth, sex
 
Patient and Cancer characteristics: 
 
Localisation: upper/lower (bladder, urethra) urinary tract
 
Cancer characteristics: histological subtype including type of variant*, PD-L1 status and FGFR alteration with type of test and CPS score.
 
 
 
Localized cancer: date of diagnosis, type of treatment (adjuvant/neoadjuvant), regimen, dates of start and end, number of ChT cycles, complete response if neoadjuvant.
 
Adv/mUC: date of diagnosis, stage at ChT initiation, metastatic sites at ChT initiation, Karnowski index and ECOG at ChT initiation, type of ChT regimen, dates of start and end, number of ChT
 
	X		X

090177e1a41aac13\Final\Final On: 28-Jul-2025 13:50 (GMT)

	cycles, response at the end of ChT, date of start of partial or complete response if so.			
Initiation of avelumab	
 
• Patients characteristics : ECOG at initiation
 
• Biological exam: neutrophil, lymphocyte, haemoglobin, creatinine clearance
 
• Metastatic sites
 
• Date of first administration, dose
 
• Use of premedication (acetaminophen and antihistamine)
 
	X		X

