5.3 SUBGROUPS

The primary and secondary objectives will be evaluated on the overall population and for prespecified subgroup.

- Main subgroup of interest: histology (UC with variant; UC without variant).
- Other subgroups of interest:
 - Histology (Pure UC; UC with variant, Pure adenocarcinoma, Other, Missing)
 - ECOG at avelumab initiation (PS 0-1; PS ≥ 2),
 - Locally advanced urothelial carcinoma versus metastatic urothelial carcinoma,
 - Previous ChT regimens (Cis/Gem, Carbo/Gem, Cis/Carbo/Gem, MVAC regimens, others),
 - Best response to 1st line chemotherapy (CR, PR, SD)
 - Regrouped best response to 1st line chemotherapy (CR+PR, SD),
 - Number of ChT cycles received in 1st line (< 4 cycles; ≥ 4 cycles and ≤ 6 ; > 6 cycles), Site of baseline metastases before ChT (visceral vs non-visceral),
 - Participants with an early relapse on avelumab and participants with a long-term response to avelumab. Patient is considered as early progressor if PFS is less than 3 months and if progression is observed. Patient is considered as long responder if PFS is equal or higher than 12 months, whatever the outcome.
This subgroup of interest will be used only for Overall Survival and progression free survival analyses, and baseline characteristics.
 - Delay between the end of ChT and the start of avelumab (< 4 weeks; between 4 and 10 weeks; > 10 weeks),
 - Delay between the end of ChT and the start of avelumab (< 4 weeks; ≥ 4 weeks),
 - ATU participants versus non ATU participants, site for the primary tumor (bladder, urethra, upper tract),
 - PD-L1 status,
 - FGFR abnormality,
 - Bajorin risk classification evaluated before ChT 1st line (0, 1, 2),
 - Presence of biological anomalies (neutropenia, lymphopenia, impaired renal function, anemia),
 - Use of concomitant treatments (corticosteroids/AIS/NSAIDs, sartans/ACE inhibitors, antibiotics, PPI) at avelumab initiation,
 - Type of subsequent treatment: Antibody-Drug Conjugate (ADC) treatment, chemotherapy, immunotherapy, targeted therapy, other. This classification will be made thanks to a medical review from Pfizer team.
 - Type of subsequent treatment: ADC versus Other.

PFIZER CONFIDENTIAL

CT24-WI-GL03-RF02 2.0 Non-Interventional Statistical Analysis Plan For Primary Data Collection Study

01-Jun-2020

Page 11 of 28

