8.2 STATISTICAL ANALYSES

All analyses will be at least provided overall and by histological status (UC with variant; UC without variant). For some effectiveness endpoints, additional subgroup analyses will be specified hereafter.

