8.2.5 Summary of analyses

Outcome	Analysis Set	Supports Protocol Objective Number	Subgroups	Statistical Method	Covariates/ Strata	Missing Data
OS	FAS	1	NA	Kaplan-Meier	NA	Excluded
OS	FAS	1	See section 5.3	Kaplan-Meier	NA	Excluded
OS 2	FAS	2	NA	Kaplan-Meier	NA	Excluded
PFS	FAS	2	NA	Kaplan-Meier	NA	Excluded
PFS 2	FAS	2	NA	Kaplan-Meier	NA	Excluded
ORR	FAS	2	NA	Descriptive statistics	NA	Excluded
DOR	FAS	2	NA	Kaplan-Meier	NA	Excluded
DOT	FAS	2	NA	Kaplan-Meier	NA	Excluded
Progression description	FAS	2	NA	Descriptive statistics	NA	Excluded
OS subsequent	FAS	2	NA	Kaplan-Meier	NA	Excluded
PFS subsequent	FAS	2	NA	Kaplan-Meier	NA	Excluded
ORR subsequent	FAS	2	NA	Descriptive statistics	NA	Excluded
DOT subsequent	FAS	2	NA	Kaplan-Meier	NA	Excluded
FBISI-18 score	FAS	2	NA	Descriptive statistics + MMRM	NA	Excluded
EQ-5D-5L score	FAS	2	NA	Descriptive statistics + MMRM	NA	Excluded
EQ-VAS score	FAS	2	NA	Descriptive statistics + MMRM	NA	Excluded
Premedication	FAS	2	NA	Descriptive statistics	NA	Excluded
Safety analyses	SAF	2	Histological group Subsequent treatment category	Descriptive statistics	NA	Excluded
Baseline characteristics	FAS & SAF	2	Progression status Subsequent treatment category	Descriptive statistics	NA	Excluded

PFIZER CONFIDENTIAL

CT24-WI-GL03-RF02 2.0 Non-Interventional Statistical Analysis Plan For Primary Data Collection Study 01-Jun-2020

Page 25 of 28

090177e19bffc15d\Approved\Approved On: 02-Dec-2022 20:57 (GMT)

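### The variant versus non-variant hazard ratio is planned only as a crude univariate estimate, so any case-mix difference would be mixed into it; one pre-specified adjusted model should support it.

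*SAP*

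**What the plan says.** - **Main subgroup.** SAP 5.3 names it: "Main subgroup of interest: histology (UC with variant; UC without variant". SAP 8.2 extends the split to everything: "All analyses will be at least provided overall and by histological status (UC with variant; UC without variant". Protocol 7 gives the reason: "Few data are available on the efficacy of immunotherapy in histology variants of adv/mUC". Protocol 5 (amendment 4) raised the target to 600 to reach the planned number of variant patients, and Protocol 9.5 sizes that group separately (47 patients).
- **Method of comparison.** SAP 8.1.3: "comparison of the different modalities to a reference level will be performed using univariate Cox proportional hazard models". The result is an HR with a 95% CI, read as a higher or lower risk than the reference level.
- **Covariates.** SAP 6.3 only points back to the subgroup list. In SAP 8.2.5 the column "Covariates/ Strata" reads NA for every outcome, including OS by subgroup.
- **Data collected.** Protocol 9.3, Table 2, includes "Patients characteristics : ECOG at initiation" and "metastatic sites at ChT initiation, Karnowski index and ECOG at ChT initiation, type of ChT regimen", as well as tumour location and response at the end of chemotherapy. SAP 5.3 also has "Bajorin risk classification evaluated before ChT 1st line (0, 1, 2". The plan uses each factor only as a one-way subgroup.
- **Other adjustment.** Protocol 9.9.1 allows an optional sensitivity adjustment for type of centre. It concerns representativeness and does not appear in the SAP.

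**The concern.** Patients with and without a variant are not randomised groups. If they also differ in performance status, extent of disease, primary site or first-line regimen, a univariate HR combines the association with histology and the association with those factors. Imbalance could produce an apparent difference, or could hide a real one.

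The study enlarges its sample and has pathology reports reviewed for this subgroup. Interim results are planned yearly for publication (SAP 3). The comparison most likely to be cited from that effort would rest on the method most exposed to case mix, although the data for a better one are already being collected.

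**Working it through.** **1. The plan's own figures.** With exponential survival and no censoring, the 95% limits for a median m are m × 2n / χ²(0.975; 2n) and m × 2n / χ²(0.025; 2n). Protocol 9.5 uses a rounded mean of 29 months, so m = 29 × ln 2 = 20.1. This gives [15.4; 27.4] for n = 47 and [18.6; 21.8] for n = 600, as stated. (With m = 20.0 exactly: [15.32; 27.22] and [18.49; 21.70].) These figures describe medians within a group. Neither document gives a precision for the variant versus non-variant HR.

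**2. Precision of that HR.** SE(log HR) = √(1/d₁ + 1/d₀), with 47 variant and 600 − 47 = 553 other patients. (SAP 2.1 still states a target of 500; the 47 belong to the 600 in Protocol 9.5.)

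- Assumed 50% dead: d = 23.5 and 276.5; SE 0.215; CI factor exp(1.96 × 0.215) = 1.52.
- Assumed 80% dead: d = 37.6 and 442.4; SE 0.170; CI factor 1.40.
- From the protocol's inputs: mean 29 months, with follow-up assumed evenly spread from 24 months (the stated minimum) to 54 months (July 2020 to the end of 2024). Fraction dead = 1 − (29/30)(e^(−24/29) − e^(−54/29)) = 1 − 0.9667 × (0.4371 − 0.1554) = 0.728. Then d = 34.2 and 402.4; SE 0.178; CI factor 1.42.

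**3. Size of a possible shift.** The documents give no prevalence by histology and no HR for any factor, so every input here is an assumption. The true histology HR is set to 1. To first order, one binary factor with HR g and prevalences p₁ (variant) and p₀ (other) multiplies the crude HR by (p₁g + 1 − p₁)/(p₀g + 1 − p₀).

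- ECOG ≥2 in 25% against 15%, g = 2: 1.25/1.15 = 1.087.
- Visceral disease in 60% against 45%, g = 1.5: 1.30/1.225 = 1.061.
- Both: 1.087 × 1.061 = 1.153.

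With long follow-up the high-risk patients die earlier and the shift shrinks. The scenarios were therefore simulated: 47 against 553 patients, median 20 months without the risk factors, censoring uniform over 24 to 42 months, 800 runs each. Between 71% and 80% of patients died.

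| Assumed imbalance (variant v other) | Crude HR | Adjusted HR | SE crude | Shift in SEs | CI excludes 1, crude / adjusted |
|---|---|---|---|---|---|
| None | 0.99 | 0.99 | 0.175 | about 0 | 4% / 5% |
| ECOG ≥2 25 v 15%, HR 2 | 1.06 | 1.00 | 0.179 | 0.3 | 7% / 5% |
| Visceral 60 v 45%, HR 1.5 | 1.06 | 1.00 | 0.176 | 0.3 | 8% / 6% |
| Both of these | 1.14 | 1.01 | 0.170 | 0.8 | 13% / 5% |
| ECOG ≥2 30 v 15%, visceral 65 v 45%, both HR 2 | 1.24 | 1.00 | 0.165 | 1.3 | 27% / 4% |

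The shift in SEs is ln(crude HR)/SE; for example ln(1.14)/0.170 = 0.131/0.170 = 0.8. Simulation error on the mean log HR is about 0.18/√800 = 0.006, so 0.99 in the first row is compatible with 1. In the fourth row the SE is 0.170 crude and 0.172 adjusted, so adjustment costs almost no precision when no covariate is missing. Imbalance in the opposite direction would move the crude HR below 1.

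**4. Room for a model.** At 0.728 × 600 ≈ 437 deaths, six parameters leave about 73 deaths each; at 50% dead, 300/6 = 50 each. Fitting is not the constraint. The roughly 34 variant deaths limit precision with or without adjustment.

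**The case against.** The study declares itself descriptive and has no hypotheses (SAP 4.1, 4.2). SAP 8.1.3 words the HR as an association, and no text in the plan attributes a difference to histology. How variant patients fare is answered by their own survival curve and median, which need no adjustment. SAP 8.2.4 tabulates baseline characteristics by histology group, and each factor gets its own HR, so an imbalance would be visible. The scenarios are hypothetical. The ECOG input in particular may be too large, because the ATU was limited to ECOG 0 or 1 (Protocol 7) and ATU patients, whose share is not stated, are a core source of the cohort. With visceral disease alone, the assumed shift is 0.3 SE.

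Most of this stands, and it limits the weight of the point. A reader might infer that the plan will report a false disadvantage for variants, or that its main-subgroup results are invalid. The documents support neither: they show no imbalance and not even its direction, and the within-group estimates stand as they are.

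What does not stand is that a descriptive label settles the matter. An HR with a CI against a reference level is a comparison. A baseline table reveals an imbalance, but a reader cannot derive an adjusted HR from it. Covariates chosen after an imbalance has been seen are also less credible than a list fixed beforehand.

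**Conclusion.** The point holds as a gap in a secondary comparison. The only planned comparison of the main subgroup is unadjusted, although prognostic factors are on file, so any case-mix difference enters the HR. Under the assumed moderate imbalances and a true HR of 1, the crude HR would lie at about 1.06 to 1.24. That is 0.3 to 0.8 SE in three of the four imbalance scenarios and 1.3 SE in the strongest, against a CI factor of about 1.4. The size depends wholly on assumed prevalences and factor HRs; with balanced case mix there is no shift. The primary OS estimate and the Kaplan-Meier medians by group are unaffected. The change is worth making because it is cheap, but it is not critical to the study's main result.

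**What to change.** 1. Keep the crude HR and label it unadjusted in tables and publications.
2. For OS and PFS in the two-level histology subgroup, pre-specify one supportive multivariable Cox model: histology; ECOG at avelumab initiation (0-1, ≥2); visceral metastases before chemotherapy (yes/no); primary site (bladder, other); and first-line regimen in collapsed plan categories that place every patient, for example cisplatin-based, carboplatin-based, both or other. Enter it in SAP 8.1.3 and 8.2.5.
3. Do not enter Bajorin class together with ECOG and visceral disease, because it overlaps with them.
4. Add best response to chemotherapy only in a second model. It may be a consequence of histology, and adjusting for it could remove part of the association of interest.
5. Report crude and adjusted HRs in the same patients, with the number lost to missing covariates by histology group.
6. Do not attribute a survival difference to histology itself on the crude HR alone.

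The cost is one extra model per endpoint (two with the second model) on data already collected, plus some loss of patients with missing covariates, which would matter most among the 47 variant patients. Unmeasured confounding remains, and a single-arm study cannot separate prognosis from treatment benefit, adjusted or not.

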#### Patients selection

In order to limit the selection bias of study patients, participating centers will be asked to include retrospectively all eligible patients from their center who had already initiated a treatment with avelumab for adv/mUC, and for the prospective part of the study, to consecutively enroll all eligible patients after study set-up, until the planned number of patients have been included in the study. All patients who died before study set-up will be included, to avoid survival bias.

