8.2.2 Secondary criteria analyses

8.2.2.1 Overall survival 2

For OS since chemotherapy initiation, endpoint will be analyzed using survival analysis method, using the same censorship as for primary criterion (Table 1), in the FAS. The starting date to be used is the date of first intake of chemotherapy as reported in the medical history. To avoid any immortal time bias between first intake of chemotherapy and the start of study treatment (avelumab), a modified Kaplan-Meier estimator will be provided using right censoring and left truncation, stabilising the estimates when small samples ($n < 5$) are present (Lai and Ying method – See section 8.1.3).

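### SAP 8.1.3 gives two different delayed-entry times for OS from first-line chemotherapy; the one beside the formula, if coded literally, would leave out deaths that occurred before inclusion

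*SAP*

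**What the plan says.** The SAP describes the entry time for this endpoint (its Overall Survival 2) in several places.

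- **SAP 8.1.3, text before the formula.** The clock starts "at a time-point preceding the study entry (avelumab start date", so study entry is equated with avelumab start. The truncated interval is then named: "Therefore, the time from 1st line of chemotherapy start date to avelumab start date is called immortal time".
- **SAP 8.1.3, text at the formula.** Survival is estimated "conditional on being free of this event at study entry", and the entry variable is defined by the words "where a represents the time from the start date to inclusion into the study".
- **SAP 8.2.2.1.** The estimator's purpose is tied to avelumab start: "To avoid any immortal time bias between first intake of chemotherapy and the start of study treatment (avelumab". The analysis is run in the FAS.

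On who belongs in the cohort, protocol 9.9.1 (Patients selection) states: "All patients who died before study set-up will be included, to avoid survival bias". SAP 2.1 also makes patients who died before study start eligible, and its third inclusion criterion has a clause for patients who died before inclusion. SAP 5.1 defines the FAS as all enrolled participants with at least one avelumab injection.

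**The concern.** For a patient who starts avelumab after the site opens, avelumab start and inclusion may nearly coincide. For a retrospective patient they need not. Access under the ATU began in July 2020 (protocol section 4, Rationale), and data collection was planned from Q2 2021 (protocol section 6). The earliest patients could therefore have been on avelumab for nine months or more before inclusion, and some would have died in between.

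The definition at the formula is the only place where the SAP defines the estimator's entry variable, so a programmer may well code from it. Patients who died before inclusion would then contribute nothing, and retrospective survivors would lose their time from avelumab start to inclusion. OS from chemotherapy would rest on fewer patients than primary OS, although both are labelled FAS. SAP 8.2 asks for all analyses by histological status, so the loss would also reach the main subgroup of interest.

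One neighbouring sentence makes this misreading easier. SAP 8.1.3 says that only participants still alive are included. That is true at avelumab start and untrue at inclusion.

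**Working it through.** **1. Effect of each definition on one record.** Let X be the time from first chemotherapy injection to death. The SAP's estimator conditions on X ≥ a. Take a hypothetical patient with chemotherapy in September 2020, avelumab in February 2021, death in April 2021 and inclusion in July 2021.

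- X = September to April = 7 months.
- Entry at avelumab start: a = 5 months. X ≥ a, so the patient is at risk from month 5 and the death counts.
- Entry at inclusion: a = 10 months. X < a, so the patient never enters the risk set.

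**2. The plan's own figure.** No precision figure is given for OS from chemotherapy. The only sizing figure is for primary OS (protocol 9.5), reproduced here as a check on the survival assumption. With median m = 29 × ln 2 = 20.10 months, the limits are 2nm/χ²(0.975; 2n) and 2nm/χ²(0.025; 2n).

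- n = 600: 18.59 to 21.81, width 3.23 (protocol: 18.6 to 21.8, width 3.2).
- n = 47: 15.40 to 27.36, width 11.96 (protocol: 15.4 to 27.4, width 12).

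**3. Simulation of the two definitions.**

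- From the documents: n = 600, median OS from avelumab 20 months, avelumab starts from July 2020, follow-up to Q4 2024, minimum risk set of 5.
- Assumed, not in the documents: retrospective share 30%, 50% or 70%; site opening 9 to 18 months after July 2020; prospective starts over the following 12 months; 4 to 8 months from chemotherapy to avelumab; inclusion lag unrelated to survival; survival either exponential or with a decreasing hazard.

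Each row is 200 runs. A is entry at avelumab start, B is entry at inclusion. Every lost patient is a death.

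| Retrospective share, survival shape | Deaths | Lost under B | Share lost | Mean median A / B (months) | SD of median A / B | SD increase |
|---|---|---|---|---|---|---|
| 30%, exponential | 432 | 36.1 | 8.4% | 23.97 / 23.96 | 1.50 / 1.67 | 11% |
| 30%, decreasing | 388 | 42.2 | 10.9% | 22.47 / 22.54 | 1.90 / 2.15 | 13% |
| 50%, exponential | 444 | 60.2 | 13.5% | 23.97 / 24.01 | 1.46 / 1.58 | 8% |
| 50%, decreasing | 396 | 69.6 | 17.6% | 22.53 / 22.67 | 1.85 / 2.21 | 19% |
| 70%, exponential | 457 | 84.0 | 18.4% | 24.21 / 24.37 | 1.48 / 1.84 | 24% |
| 70%, decreasing | 405 | 97.7 | 24.1% | 22.43 / 22.41 | 1.75 / 2.99 | 71% |

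The SD increase is B/A − 1; for example, 1.67/1.50 − 1 = 11%. With 200 runs, an SD carries a relative error of roughly 1/√(2 × 199) = 5%, so only the direction and rough size should be read. The median hardly moves because person-time before inclusion is dropped together with the deaths.

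**4. Second set of assumptions, and the variant subgroup.** Here inclusion falls 0 to 14 months after avelumab start and follow-up is 24 to 54 months.

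- n = 600: about 50 of 437 deaths (11%) are lost at a 40% retrospective share, and 74 of 453 (16%) at 60%. The SD of the median goes from 1.62 to 1.84 and from 1.37 to 1.80 months.
- n = 47, the variant count in protocol 9.5: about 4 to 6 of 34 to 36 deaths are lost. The SD goes from 4.66 to 5.07 and from 4.46 to 5.20 months.

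**The case against.** The strongest reply is that the SAP already answers the question. Just before the formula it equates study entry with avelumab start and defines the truncated interval as chemotherapy start to avelumab start. The sentence holding the disputed clause conditions on study entry, the term just defined. SAP 8.2.2.1 says the immortal time to be removed lies "between first intake of chemotherapy and the start of study treatment (avelumab". On this view the clause is a loose restatement. The subsection also seems to use inclusion in that loose sense when it says that only living participants are included. In addition, the median does not move materially even on the literal reading, and the endpoint is secondary in a purely descriptive study.

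Much of this stands. The intent is avelumab start, and the consequence depends on how the formula is coded. The SAP does not say how a record with entry after death is to be handled; the exclusion follows from the estimator's own condition.

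The reply does not remove the contradiction. SAP 2.1 and the inclusion criteria use inclusion for enrolment, an event that can come after death, so the clause has a definite meaning in these documents and it is the wrong one for this estimator.

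**Conclusion.** SAP 8.1.3 contradicts itself on the delayed-entry time for OS from first-line chemotherapy, with a risk of misprogramming. Under the assumptions shown, coding from the definition at the formula would lose about 8% to 24% of deaths. The SD of the estimated median would rise by 8% to 24% in five of the six scenarios and by 71% in the sixth. The retrospective share, the lags and the survival shapes are assumed, so these figures illustrate the risk and do not describe this cohort.

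A reader might infer three stronger conclusions, and none is supported:

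- **That the SAP sets entry at inclusion and discards the earlier deaths.** The text before the formula and SAP 8.2.2.1 both say avelumab start.
- **That the estimated median would be biased.** In the simulations it shows little or no shift. That rests on delayed entry also being applied to survivors and on the inclusion lag being unrelated to survival.
- **That primary OS is affected.** Primary OS starts at the first avelumab injection and does not use this estimator.

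**What to change.** In SAP 8.1.3:

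1. Define the entry time as the time from first injection of first-line chemotherapy to first injection of avelumab, for every participant, retrospective or prospective, and delete the reference to inclusion in the study.
2. Reword the sentence on living participants so that it says they are alive at avelumab start.
3. Use a different symbol for the exponent in the Lai-Ying modification, which currently shares the letter a with the entry time.

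The cost is a few words of SAP text. No new data are needed, because protocol 9.3, Table 2 already collects the chemotherapy start date and the date of first avelumab administration. The change follows the purpose stated in SAP 8.2.2.1 and keeps every FAS death in the analysis.
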